1. INTRODUCTION

The ability to diagnose and treat cancer at early stages has led to an increased number of cancer survivors, and this has prompted the study of behavioral and pharmacologic interventions for improving survival and quality of life in cancer survivors.

Insulin-like growth factor-1 (IGF-1) is a central biomarker of interest for the study of interventions in survivors of solid tumors, and is associated with increased risk of several common cancers including breast, colorectal, prostate, and lung.¹ Some studies suggest higher IGF-1 levels are associated with higher mortality in patients with cancer,² and it has been hypothesized that reducing IGF-1 might prevent cancer in persons without cancer (primary prevention) and cancer recurrence among cancer survivors (secondary prevention).

IGF-1 is a mitogen that promotes cell-cycle progression and cellular transformation by rapid cell turnover. Over 80% of IGF-1 circulating in blood is bound to the insulin-like binding protein (IGFBP)-3. Two putative strategies that might lower IGF-1 include pharmacologic (e.g., metformin) and non-pharmacologic (e.g., weight loss) approaches. Metformin and weight loss are particularly appealing interventions, given their beneficial effects in treating other conditions, their widespread use, and their well-documented safety profiles.

Metformin is associated with decreased risk of several types of cancer in patients with diabetes³⁻⁵. There are multiple mechanisms by which metformin might inhibit cancer development and growth. In addition to its effects on glucose lowering and insulin sensitivity,⁶ preliminary evidence suggests that metformin may decrease circulating levels of IGF-I and other growth factors.

While the relationship of IGF-1 with adiposity is inconsistent,⁷⁻⁹ there is a positive association between IGFBP-3 (reflective of bound IGF-1) and BMI, indicating lower biologically active IGF1 levels among obese women.¹⁰ Also, lifestyle changes including weight loss and other healthy behaviors have also been shown to improve insulin sensitivity

In this context, we propose a randomized, 3-arm trial to compare the effects of self-directed weight loss, coach-directed weight loss, and metformin treatment on IGF-1 and the IGF-1 to IGFBP3 ratio. This trial will enroll ~120 cancer survivors (~50% female, ~50% African American) who will be randomized to one of 3 arms:

A. Self-Directed Weight Loss

B. Coach-Directed Behavioral Weight loss

C. Metformin Treatment

The duration of intervention and follow-up will be 12 months. The primary outcomes will be changes in IGF-1 and the IGF-1:IGFBP-3 ratio at 6 months. Primary outcome assessment will occur at 6 months to maximize data collection at the time of the most anticipated weight loss and to minimize a decrease in sample size due to censoring from recurrent cancer. However, data from 12 months will also be reported.

2. SPECIFIC AIMS

Primary Aims

- 1) Test the hypothesis that participants in the coach-directed behavioral weight loss arm will experience greater decreases in IGF-1 and IGF-1:IGFBP3 than those in the self-directed weight loss arm at 6 months.
- 2) Test the hypothesis that participants in the metformin arm will experience greater decreases in IGF-1 and IGF-1:IGFBP3 than those in the self-directed weight loss arm at 6 months.

Secondary Aims

- 3) Test the hypothesis that participants in the metformin arm will experience greater decreases in IGF-1 and IGF-1:IGFBP3 than those in the coach-directed behavioral weight loss arm at 6 months.
- 4) Determine the effects of coach-directed behavioral weight loss and metformin separately on IGF-1 and IGF-1:IGFBP3 at 12 months (Aims 1 – 3 at 12 months)
- 5) Determine the effects of coach-directed behavioral weight loss and metformin separately on the following outcomes at 6 and 12 months:
 - Weight, Body Mass Index
 - EuroQol
 - Dietary intake and physical activity
 - Glucose, insulin, hemoglobin A1c
 - IL-6, IL-8, CRP
 - Side effects questionnaire
- 6) Conduct exploratory analyses (Aims 1 – 5 above) in key, pre-specified subgroups, defined by sex, race, type of cancer, and baseline levels of IGF-I and the IGF-1: IGFBP-3 ratio.

- 7) Explore the association of physical activity levels with IGF-1 and the IGF-1: IGFBP-3 ratio.
- 8) Collect and store specimens of blood and stool for other assays. Candidate assays include leptin, adiponectin, VEGF, HGF, and EGF, SLC22A1, SLC22A2, and SLC47A1 gene variants and 16S bacterial whole genome sequencing (stool).

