8.3 Metformin Pharmacologic Intervention

Participants in this arm will continue to receive care from their primary care provider and/or oncologist and/or other providers. Participants in this arm will receive medication-related education and counseling from a study staff member immediately following randomization. Participants will receive metformin, an oral medication for type 2 diabetes. It primarily reduces hepatic production of glucose without increasing insulin secretion. Metformin is not currently approved for use as a cancer prevention medication. This study is designed to investigate its efficacy in reducing Insulin-like Growth Factor 1(IGF-1) and IGFBP-III, which in turn may reduce cancer cell growth among cancer survivors. This study is not intended to study the treatment of cancer or prevention of cancer recurrence with metformin. An application for an IND waiver has been submitted, and approved by FDA. FDA granted the approval to use this product for an indication that is not FDA-approved.

Participants randomized to the metformin intervention will receive metformin up to 2,000 mg per day.⁸⁶ Dosing can be flexible, two or three times per day with meals as tolerated for 12 months. See Section 5.2 for exclusion criteria.

Metformin is primarily excreted by the kidney, and the risk of adverse events, although low, increases in patient with impaired renal function. Because aging is associated with reduced renal function, the FDA recommends “treatment should not be initiated in patients ≥ 80 years of age unless measurement of creatinine clearance demonstrates that renal function is not reduced “. Because we will measure kidney function and estimate GFR, we will be excluded based on renal function rather than age.⁸⁶ In this fashion, we will increase the opportunity for older individuals to participate in this trial.

Dosing

Oral titration of metformin in an open-label fashion will occur as follows:

- 1) 500 mg by mouth once daily with breakfast for 7 days or longer if needed for tolerance;
- 2) If tolerated, increase metformin to 500mg by mouth twice daily with breakfast and dinner for 7 days or longer if needed for tolerance;
- 3) If tolerated, increase metformin to 1000 mg by mouth in the morning and 1000 mg in the evening for 7 days or longer if needed for tolerance;

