Assessing participants' adherence to metformin and identifying non-adherent participants will help optimize adherence to the prescribed medicine. Participants in the metformin arm will receive one-on-one education with study staff at baseline and educational materials covering common side effects, administration of metformin, and contact information of study staff and physician. In addition to scheduled face-to-face data collection visits, follow-up phone calls at 2 week and 1 month will be conducted by trained study staff on a one-to-one basis to ensure adherence and address questions. The following are methods to assess adherence among metformin arm participants:

- Pill count by visual inspection during visits when participants bring their containers for refill. In the absence of pill containers, participants will be interviewed about their pill compliance.
- Follow-up phone calls at 2nd week and 1 month. Participants will be instructed to contact study staff if they experience any side effects, especially gastrointestinal symptoms such as nausea and diarrhea.

9. VISITS AND FOLLOW-UP Approach to Data Collection and Visits

Study investigators and staff recognize the need to accommodate participant needs and accordingly will be flexible in implementing the expected data collection procedures. For example, some participants may need to split visits (e.g. having 2 baseline visits), while others might prefer to bundle data collection into fewer visits (e.g. bundling screening and baseline visits). Our general approach will be to accommodate such requests, as long as we collect the required data.

Pre-Screening Call

Recruitment materials will direct interested individuals to contact the study by e-mail, postcard, or the telephone contact information provided in the mailed recruitment materials. A pre-screening phone call will then occur. During the phone call, study staff will provide information about the trial, obtain verbal informed consent, and collect data on eligibility.

Screening Visit 1

Those who remain interested and potentially eligible will be asked to attend the first screening visit in the clinic center in person and meet with study staff. Trained study staff will obtain the following measures:

- Weight & height
- Blood pressure
- non-fasting labs
- Questionnaires (See Table 3)

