All potential participants will demonstrate the ability to send and receive emails, ability to complete online forms, and sufficient phone minutes for coaching calls during this visit.

Screening Visit 2

Participants, who remain eligible after the screening visit 1, will be asked to attend the second screening visit after at least 9 hours of fasting. The following activities and measurements will take place:

- Orient the participant about each intervention arm, expectations and related details. -
Weight
- Blood pressure
- Fasting labs
- HbA1c
- Current medication
- Questionnaires (See Table 3)

Randomization Visit

During this visit, study staff will reconfirm the eligibility. Weight and blood pressure will be measured. Each participant will be re-oriented to each intervention arm. Each participant will be randomized and assigned to one of the three interventions arm: self-directed weight loss, coach-directed behavioral weight loss or metformin.

Follow-Up Visits

There are three types of follow-up based on the contact mode: in-person, telephone and website.

In-person follow-up visits will take place at ProHealth at 3-month, 6-month, and 12-month intervals. Participants will be asked to attend those visits after having fasted for at least 9 hours. The following will take place during these visits:

- Weight
- Blood pressure
- Fasting labs and HbA1c
- Patient reported outcomes (EuroQol;)
- Current medication

- Fat screener, fruit screener, physical activities, general symptoms form
- Pill counts for adherence, challenges and enabling factors for adherence
- Any adverse events
- Any other issues raised by the participant that can be addressed within the scope of the study

Additional telephone contacts, for the metformin arm, will take place at the following times after baseline visit: every 2 weeks for the first month and otherwise as needed throughout the intervention period. During these calls, the study staff will ask about adherence and side effects using a standardized study questionnaire.

Throughout the study, email and web contacts will take place to remind participants in the coach-directed behavioral weight loss arm to enter their self-monitoring data, and to followup on adherence and check for adverse events. In-person visits will take place on the 3rd, 6th and the twelfth month for the same reasons.

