Interim events will be ascertained every three months, and serious adverse events will be reported per institutional review board and FDA regulations.

Safety Monitoring and Measures to Reduce Potential Drug-Related Side Effects

Standard laboratory studies will be done for each participant in the metformin arm. eGFR and complete blood count will be measured for eligibility. A complete blood count, and basic metabolic panel (including eGFR) will be measured at 12 months.

The most common side effects, reported by 28% of persons taking metformin, are gastrointestinal symptoms, among which nausea, diarrhea, abdominal bloating, metallic taste, anorexia, or flatulence are included.⁶³ These side effects are usually transient and resolve spontaneously or can be controlled by graduate dosing. Rarely, metformin can cause lactic acidosis among persons with renal or hepatic insufficiency, especially during episodes of hypoxia or circulatory failure. In addition, about 6-9% persons on metformin develop reduced vitamin B12 levels.⁸⁶

Potential risks associated with **blood** draw procedure and measures to minimize potential risks

A- Blood draw may produce discomfort, pain, bruises, and rarely, infection, syncope, or bleeding. Out trained staff will follow standard phlebotomy protocol for infection prevention and control, safety equipment and best practices.

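### Side effects are compared between arms only at 6 and 12 months, and the related-only adverse event table does not fill the gap for earlier, transient GI symptoms

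*Combined protocol and SAP*

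**What the plan says.** Aim 5 in Section 2 is to "Determine the effects of coach-directed behavioral weight loss and metformin separately on the following outcomes at 6 and 12 months", and a side effects questionnaire is on its list. Section 17.2 places the secondary contrasts at 6 and 12 months. Its mixed model does contain group-by-3-month terms for outcomes measured at that visit, but the text says that these serve estimation and that the 3-month effect is neither a primary nor a secondary goal. Side effects appear in neither of its example lists (outcomes with and without 3-month data).

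On timing, Section 8.3 titrates metformin on GI tolerance in three steps, the first being "500 mg by mouth once daily with breakfast for 7 days or longer if needed for tolerance". Section 13.2 says of the GI effects: "These side effects are usually transient and resolve spontaneously or can be controlled by graduate dosing".

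Early data are collected. Section 9 lists adverse events and "Fat screener, fruit screener, physical activities, general symptoms form" at the 3-, 6- and 12-month visits. Section 13.1 collects adverse events at every in-person visit. Table 3 has interim events at 3, 6 and 12 months for all participants, and Section 13.2 adds "Interim events will be ascertained every three months". Section 11 masks follow-up data collectors to assignment. The metformin arm alone also has calls in the first month: "During these calls, the study staff will ask about adherence and side effects using a standardized study questionnaire".

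On reporting, Section 13.1 tabulates only adverse events rated at least possibly related to the study interventions. The relatedness categories that follow are defined by timing and response pattern relative to the investigational drug or agent.

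**The concern.** If GI symptoms cluster around titration and then fade, a first comparison at 6 months falls after most of them. It answers whether symptoms persist or arise later. It may not answer how many participants were affected at any time, which also matters for a drug offered to cancer survivors without medication-treated diabetes.

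The adverse event table is the natural place to look for the missing information, but it is filtered by attribution to the drug. A participant in a comparison arm takes no study drug, so a GI symptom there can hardly meet those definitions. The same symptom on metformin usually would. The table therefore gives no fair comparator rate, and the plan does not say that it will be laid out by arm or by visit.

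**Working it through.** The plan states no figure for this point, so there is none to reproduce. The check covers timing, then an illustration under labelled assumptions.

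**Timing.** Visits are taken as day 91 and day 182.
- Fastest titration (Section 8.3): 3 × 7 = 21 days.
- Gap to the 3-month visit: (91 − 21)/7 = 10 weeks. Gap to the 6-month visit: (182 − 21)/7 = 23 weeks.
- For titration to last until the visit, each step would need 91/3 ≈ 30 days (3 months) or 182/3 ≈ 61 days (6 months).

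Even slow titration would thus normally end well before the first planned contrast. The 3-month visit is the first scheduled point after titration at which adverse and interim events are collected in every arm.

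**Illustration.** Section 13.2 gives 28% with GI side effects on metformin, without a time frame; it is treated here as the proportion ever affected. Background rate *b* and fraction *r* of the excess resolved by 6 months are assumptions.
- 6-month difference = (0.28 − b)(1 − r). Dilution against the early difference = r(0.28 − b).
- 95% half-width = 1.96 × √[(p₁(1 − p₁) + b(1 − b))/n], with n = 40, or n = 40 × 0.8 = 32 under the 20% attrition in Section 16.

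| b | Early difference (r = 0) | r = 25% | r = 50% | r = 75% | Early half-width, n = 40 | n = 32 |
|---|---|---|---|---|---|---|
| 5% | 23 | 17.3 | 11.5 | 5.8 | 15.5 | 17.3 |
| 10% | 18 | 13.5 | 9 | 4.5 | 16.7 | 18.7 |
| 15% | 13 | 9.8 | 6.5 | 3.3 | 17.8 | 19.9 |

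(Percentage points.) With 40 per arm the early interval excludes zero at backgrounds of 5% and 10%; with 32, only at 5%. At b = 10% and r = 50%, the 6-month half-widths are 15.3 (n = 40) and 17.1 (n = 32).

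**Bias of the remedy.** Suppose metformin participants report every early symptom and comparison participants only a fraction *s*. The early difference is then overstated by b(1 − s). For b = 5%, 10%, 15%:
- s = 85%: 0.75, 1.5, 2.25 points
- s = 70%: 1.5, 3.0, 4.5 points
- s = 50%: 2.5, 5.0, 7.5 points

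Over the grid of 4 resolution × 3 background × 3 recall levels, this overstatement exceeds the dilution in 13 of 36 cells: all nine with nothing resolved, three at 25% resolved, one at 50% (7.5 against 6.5 points, at b = 15% and s = 50%) and none at 75%. Leaving out the cells with nothing resolved, it is 4 of 27.

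**The case against.** The strongest reply is that the time points are a declared choice. Section 17.2 disclaims the 3-month effect openly, and tolerability at 6 and 12 months is a legitimate question for a 12-month intervention. Metformin may also be stopped and restarted (Section 8.3), so GI exposure is not confined to the first weeks. This stands: the point is an improvement in reporting and not an error.

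A reader might infer that no analysis uses 3-month symptom data. That is too firm. The Section 17.2 list of outcomes with 3-month data is open-ended, so a symptom score could enter the model. What is missing is a declared 3-month contrast or summary.

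A reader might also infer that the general symptoms form already supplies comparable GI data in every arm. The documents do not establish this. The form appears only in the Section 9 visit list, which also contains pill counts, a metformin-arm item. It is absent from Table 3, its content and recall period are not given, and nothing identifies it as the Aim 5 questionnaire. With short recall it would itself miss symptoms that ended weeks before month 3. Adverse and interim events are the firmer all-arm source.

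It can be said that known metformin GI effects would normally be rated probably related even when another cause may exist, and so be tabulated. That is fair for the metformin arm, but it leaves the comparator rate missing.

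Finally, participants are unblinded and attention is unequal: "Participants in the metformin arm will receive one-on-one education with study staff at baseline and educational materials covering common side effects", and "Additional telephone contacts, for the metformin arm, will take place at the following times after baseline visit". Differential recall or reporting is a real possibility, and under some assumptions it is as large as the dilution removed.

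**Conclusion.** The point holds as a minor, inexpensive improvement. As planned, the between-arm comparison of side effects mainly describes symptoms that persist or arise later, unless the questionnaire's recall reaches back to randomization. The related-only adverse event table does not supply the earlier comparison.

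The size of any understatement cannot be derived from the documents: the 28% has no time frame, and no background or resolution rate is stated. Under the assumptions above, the difference lost by 6 months runs from nothing to 23 − 5.75 = 17.25 points. The early estimate would carry an interval of about ±15 to ±20 points. The gain is a fuller description and not assured significance.

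A reader might infer that early side effects go uncollected, that participants are less safe, or that the IGF-1 results are affected. None of these follows. Early events are recorded in all arms, the metformin arm is called in the first month, safety monitoring does not depend on Aim 5, and the IGF-1 analyses do not use these data.

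**What to change.** In Sections 13.1 and 17.2, and by reference in Aim 5:
- Tabulate GI adverse events and GI interim events by arm, regardless of judged relatedness, at 3, 6 and 12 months and as the cumulative proportion with any event. Give 95% intervals and the number of participants behind each figure. Keep the related-only table alongside.
- Name the form that serves as the Aim 5 side effects questionnaire and state its recall period.
- If the general symptoms form has GI items, add its 3-month results descriptively by arm, with the recall period stated.
- Report the metformin-arm call findings separately and keep them out of any between-arm proportion, since no other arm is called about side effects.
- State beside the tables that participants were unblinded and that only the metformin arm was counselled and called about side effects.

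The cost is SAP wording, one or two more descriptive tables and a check of one existing form. There is no new visit and no change to alpha or sample size. The downsides are wide intervals and possible differential recall or reporting.

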17.2 General Statistical Approach

The primary endpoint of this trial is the 6-month change in level of IGF-1 and IGF1 to IGFBP-III ratio among the Coach-Directed Behavioral Weight Loss arm versus self-direct arm (B vs. A), and metformin arm compared to self-direct arm (C vs. A). Intervention effects will be analyzed using intent-to-treat. Each active intervention arm will be compared with the control arm using

likelihood based mixed effects linear regression models utilizing data from all 3 time points, i.e. baseline, 6, and 12 months, simultaneously, as following.

The primary analysis model: The mean model for the mixed effects regression will be structured to include 2 binary intervention arm indicators (for Group B and C), 3 binary followup time indicators (for 3-, 6- and 12-month follow-up), and the cross-product interaction terms between the group and time indicators (6 interaction terms), and the covariance model will employ a 4x4 unstructured covariance matrix to allow different outcome variances and account for the intra-individual outcome correlations over time. Race and baseline BMI levels, the variables used for stratifying the randomization, will be included in the mean model. Other variables found not to be balanced between the trial arms will also be included as necessary. Outcomes may be transformed as needed to satisfy the distributional assumptions for the likelihood approach.

The primary testing contrasts of this trial will be the 2 aforementioned pairwise comparisons at 6 months, which will be evaluated through the regression coefficients of the Group B by 6month interaction term (B vs. A), and Group C by 6-month interaction term (C vs. A), respectively. The secondary testing contrasts include B vs. C of change in outcomes at 6month, and the 3 pairwise group comparisons of outcome changes at 12 months, which will be evaluated using the same model through the corresponding group by time interaction terms.

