For outcomes such as IGF-1, IGF-1:IGFBP3 ratio, weight, BMI, and measures assessed through the metabolic panel labs, where data will be available at 3-month, these information will be utilized through the primary model to enhance model estimation, especially in the event of missing data encountered at 6- and/or 12-month, events though the effect size of the intervention at 3-month is not part of the primary or secondary goals. For outcomes such as EQ-5D, questionnaire outcomes on dietary intake and physical activity, HbA1c, IL-6, IL-8, and CRP, where data will not be available at the 3-month visit, the analysis models will not include any independent variables terms related to that visit.

We will also conduct subgroup analyses to explore for potential differential intervention effects across these pre-specified subgroups. Statistical significance of these subgroup analyses will be evaluated though incorporating appropriate subgroup by intervention by visit interaction terms. To explore the association of physical activity levels with the outcomes of IGF-1 or the IGF-1: IGFBP-3 ratio, time dependent physical activity measures will be further included to augment the primary analysis model to explore for the degree of attenuation of intervention effect by physical activities. Similar analyses could be done for body weight and BMI.

We will also explore for possible treatment effect modification by baseline BMI level to better understand the potential heterogeneity of treatment effects to inform future trials and studies. This will be carried out by including the 3-way interaction terms (Group indicator by Time indicator by BMI) in the primary analysis model. We will also estimate total intervention costs for future trials in a large population.

Missing and incomplete data

Prevention is far superior to a statistical cure, and every effort will be made to collect outcome data on all randomized participants. For example, we will collect outcomes on individuals who have stopped participating in the trial intervention. Due to the high longitudinal correlation, missed “interior” visits won’t decrease information very much for a linear trend. However, they are needed to assess departures from a linear trend.

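### Aim 6 examines effect modification by baseline IGF-1 and the baseline ratio through subgroups with no stated cut-points; a continuous baseline covariate would be more efficient for the two matched analyses

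*Combined protocol and SAP*

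**What the plan says.** Section 2, Aim 6: "Conduct exploratory analyses (Aims 1 – 5 above) in key, pre-specified subgroups", which are "defined by sex, race, type of cancer, and baseline levels of IGF-I and the IGF-1: IGFBP-3 ratio". Two of the five subgroup factors are the baseline values of the two primary outcomes, IGF-1 and the IGF-1:IGFBP-3 ratio. Both are continuous.

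Section 17.2 on testing: "Statistical significance of these subgroup analyses will be evaluated though incorporating appropriate subgroup by intervention by visit interaction terms".

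Section 17.2 on the primary model: the mean has arm indicators, indicators for the 3-, 6- and 12-month visits, and their products, so baseline is the reference visit. In addition, "the covariance model will employ a 4x4 unstructured covariance matrix". The opening of the same section counts visits differently ("utilizing data from all 3 time points, i.e. baseline, 6, and 12 months, simultaneously"), but on either count baseline is a response.

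The documents do not give cut-points or a number of groups for baseline IGF-1 or the ratio. They do not say whether either could enter as a continuous value, and they do not move baseline from response to covariate for this analysis.

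**The concern.** Aim 6 is how the trial would learn whether people who start with high IGF-1, or a high ratio, respond more. Section 17.2 wants heterogeneity of effect explored to inform later studies. Cutting a continuous modifier into groups weakens that search, and the size of the loss depends on cut-points that have not been fixed although the subgroups are called pre-specified. If they are chosen after the data are seen, the choice can shape the result.

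The model adds a practical trap. An analyst who prefers the continuous value might add it, with its main effect, to the four-response model. For the matched outcome the covariate is then identical to the first response.

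**Working it through.** **Inputs.** From section 16: SD 60 ng/ml and correlation 0.90 for IGF-1; SD 11 and 0.80 for the ratio; 40 per arm; 20% attrition (32 per arm). Assumed here: two-sided 0.05 for the interaction, a normal baseline, linear modification, and one active arm against control.

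**The plan's own figure.** No power or precision is stated for Aim 6. The nearest figure is the detectable main effect of 17.4 ng/ml. The stated inputs give (2.241 + 0.842) × 60 × √(2 × 0.10) × √(2/40) = 18.5, so 17.4 is not reproduced. It serves below only as a scale for an assumed slope, and nothing here depends on the gap.

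**1. Validity.** With no modification, the simulated rejection rate was about 5% for both the continuous and the grouped tests. Regression to the mean is the same in randomised arms and cancels in the interaction.

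**2. Information kept by grouping.** For a linear modifier this is the variance between group means divided by the total variance. At a median split of a normal variable the group means lie at ±SD × √(2/π), so the share kept is 2/π = 0.637 and the loss is 36%.

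| Grouping | Loss |
|---|---|
| Quartiles, scored | 14% |
| Tertiles, scored | 21% |
| Median split | 36% |
| 33/67 split | 41% |
| 25/75 split | 46% |
| 20/80 split | 51% |

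Scored means one trend term across the groups. If baseline IGF-1 is lognormal with SD 60 and an assumed mean of 120 to 200 ng/ml, a median split loses 41% to 47%.

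**3. What modelling change adds.** Residual variance given continuous baseline is 60² × (1 − 0.90²) = 684. For change within median halves it is 684 + 0.10² × 60² × (1 − 2/π) = 697.1. The share kept falls from 0.637 to 0.637 × 684/697.1 = 0.625. For the ratio the result is 0.612. Almost all of the loss therefore comes from grouping.

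**4. Power at a large assumed slope.** Take 17.4 ng/ml per SD, that is 17.4/60 = 0.29 per ng/ml, with a critical t on 76 df of 1.992.
- Continuous: SE ≈ √(0.19 × 2/37) = 0.101, where 37 = 40 − 3 allows for the estimated spread of baseline. Then 0.29/0.1013 = 2.86 and power ≈ Φ(2.86 − 1.99) = 81%.
- Median split: the halves differ in effect by 17.4 × 2√(2/π) = 27.8. Within-half variance is 697.1 in control and 684 + 0.39² × 60² × (1 − 2/π) = 883 in the active arm. With 20 per cell, SE = √((697.1 + 883) × 2/20) = 12.57. Power ≈ Φ(27.8/12.57 − 1.99) = 59%.

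Simulation agrees: about 81% continuous, 69% scored tertiles and 58% median split. With 32 per arm, repeated simulations gave 70% to 72% against 45% to 48%.

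**5. Power at a modest slope.** Section 16 equates 17.4 ng/ml with about a 10% reduction. A constant 10% effect implies a slope of 0.10 per ng/ml. Continuous: 0.10/0.1013 = 0.99 and Φ(0.99 − 1.99) ≈ 16%. Median split: about 11% in simulation. With 32 per arm it is 14% against 10%.

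**6. Detectable subgroup difference.** At a median split with 40 per arm, SE = √(697.1 × 4/20) = 11.81. The detectable difference between halves is (1.960 + 0.842) × 11.81 = 33.1 ng/ml. For the ratio it is 8.4.

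**7. Continuous baseline in the four-response model.** With its main effect and interactions in the mean, for the same outcome, the fitted baseline residual variance was zero to machine precision (about 10⁻²⁶). The 4x4 covariance is then singular and the likelihood unbounded. With a median split, or with the baseline ratio as modifier of IGF-1, the matrix had full rank.

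**The case against.** The strongest reply is that Aim 6 is exploratory, the grouped test holds its size, and no primary or secondary contrast depends on it. All of that stands. Groups also avoid assuming linearity, and section 3.4 cites a non-linear relation between BMI and IGF-1, so a ban on cut-points would go too far.

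The power example is also generous. If the average effect is 17.4 ng/ml, a slope of 17.4 per SD means no effect at 1 SD below the mean and 34.8 at 1 SD above. At the modest slope neither method answers the question. That stands too, and limits what the change can deliver.

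A reader might infer that the planned analysis cannot be fitted. The documents do not support this: they plan subgroups, and the grouped model has full rank. The singular fit belongs to a model nobody has proposed, and only where outcome and modifier are the same variable. Cross pairs and the Aim 5 outcomes are untouched. Even in the matched case, a version with only follow-up arm-by-visit-by-baseline terms and no common baseline slope can be identified. Nor can one argue that BMI sets a continuous precedent: section 17.2 refers to baseline BMI levels used in stratification and never says BMI enters continuously.

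What survives is that the planned method is less efficient than a simple alternative using the same data, and that its groups are undefined.

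**Conclusion.** The point holds as an efficiency and specification improvement to an exploratory analysis. It is not an error in the trial's main inference. Grouping loses about 36% of the information at a median split under normality and linearity, and roughly 14% to 51% across the groupings examined. A reader might take about a third as the plan's loss, but that rests on a median split the documents never state. At the large assumed slope the gain is worthwhile (about 81% against 58%, or 69% with scored tertiles); at 0.10 per ng/ml it is trivial (16% against 11%). These figures assume full follow-up, a single active-control comparison and a two-sided 0.05 test, a level the plan does not state for Aim 6.

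**What to change.** For IGF-1 by baseline IGF-1, and for the ratio by baseline ratio, state in section 17.2:

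- The main exploratory test uses the 3-, 6- and 12-month values as responses with a 3x3 unstructured covariance. Centred continuous baseline is a covariate, with baseline-by-visit, arm-by-visit and arm-by-visit-by-baseline terms.
- The 6-month three-way terms are tested for each active arm against self-directed weight loss. Arm effects are reported with intervals at the 25th, 50th and 75th percentiles of baseline.
- Continuous baseline, with its main effect, is not added to the four-response model for the same outcome.
- Subgroup estimates may be shown, with the number of groups and cut-points fixed in advance.
- Linearity is checked with a plot or spline.

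For the cross pairs and Aim 5 outcomes the four-response structure can stay. It would help to add that power for modest modification is low, so that a null interaction is not read as absence of modification.

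The cost is SAP wording and one extra model per outcome, with no new data. The downside is the linearity assumption, which can be checked.
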